## **3 INVESTIGATIONAL PLAN**

This study will be a multi-institutional field test for the IMPACT. The survey will be administered to maxillofacial trauma patients presenting for routine clinic follow-up along with a control QOL survey. IMPACT module and subscale scores will undergo psychometric testing to determine validity and reliability.

### **3.1 General Schema of Study Design**

This will be prospective, observational survey study for patients with maxillofacial trauma.

### **3.2 Study Duration, Enrollment and Number of Sites**

#### **3.2.1 Duration of Study Participation**

The study duration per subject will be up to 3 months, with 1 day of screening and initial survey completion, then 1 additional follow-up survey at a subsequent appointment. Each survey takes 2-20 minutes to complete depending on complexity of the fracture pattern, for a possible total study commitment of 4-40 minutes for each participant.

#### **3.2.2 Total Number of Study Sites/Total Number of Subjects Projected**

The study will be conducted at approximately 10 investigative sites across the United States. Recruitment will stop when 150 subjects have completed each IMPACT Module. It is expected that approximately 500 subjects will be enrolled to yield 150 subjects that are indicated for each IMPACT module.

### **3.3 Study Population**

Participants will be identified from the population of patients presenting to clinics where facial trauma is managed, including otolaryngology, oral and maxillofacial surgery, plastic surgery, and/or ophthalmology clinic(s).

---

---

### **3.3.1 Inclusion Criteria**

- 1) Diagnosis of maxillofacial trauma (fracture of any facial bone[s] and/or soft tissue injury) within 12 months of recruitment date.

### **3.3.2 Exclusion Criteria**

- 1) Patients presenting to clinic for reasons not related to maxillofacial trauma.
- 2) Patients with isolated fractures of the cranium or teeth.
- 3) Patients who cannot read, write, and/or speak English.
- 4) Patients who are unable to provide informed consent for themselves (including those who are under 18 years old, incapacitated, intoxicated, or cognitively impaired with a legal guardian)

Subjects that do not meet all of the enrollment criteria may not be enrolled. Any violations of these criteria must be reported in accordance with IRB Policies and Procedures.

---

## **4 STUDY PROCEDURES**

This study is observational and will not involve any change to the routine clinical care of participants. The three components of data collection in this study will be the (1) initial visit (screening, informed consent, and initial survey completion), (2) the follow-up visit (follow-up survey completion), and (3) a chart review for independent variables.

### **4.1 Observational Period**

All patients presenting to clinic for maxillofacial trauma will be screened using the inclusion and exclusion criteria above. Patients who satisfy these criteria will be asked to complete surveys at two consecutive appointments during any of their regular clinical follow-up for maxillofacial trauma within one year from the injury.

#### **4.1.1 Procedures: Initial Visit**

Informed Consent: Patients will be introduced to the study and asked to complete informed consent. Those who do not wish to participate will not be given the surveys and will undergo the routine clinical care as otherwise scheduled.

IMPACT and 15D Survey Completion: A member of the research team will assign and administer the appropriate IMPACT modules for each patient based their fracture pattern (preferably on a tablet, but may complete on paper if needed). All patients will also complete the 15D QOL survey at each visit.

#### **4.1.2 Procedures: Follow-up Visit**

IMPACT and 15D Survey Completion: A member of the research team will assign and administer the appropriate IMPACT modules for each patient based their fracture pattern (preferably on a tablet, but may complete on paper if needed). Alternatively, patients will be

---

offered the opportunity to provide their email address to complete the follow-up survey at home at a later date.

## **4.2 Subject Completion/Withdrawal**

Patients may choose to discontinue participation at any time without prejudice to their clinical care. For patients that choose to withdraw, no further surveys will be collected.

### **4.2.1 Early Termination Study Visit**

For patients that choose to withdraw, no further surveys will be collected. They will be asked if any previously collected data may still be used anonymously. If yes, that data will be included in the analysis but if not, all prior survey responses and other data will be permanently deleted from the database.

---

---

## 5 STUDY EVALUATIONS AND MEASUREMENTS

### 5.1 Screening and Monitoring Evaluations and Measurements

#### 5.1.1 IMPACT Survey

The IMPACT is a PROM with 4 independent modules. The first is a “General Module” for all patients with maxillofacial trauma. The remaining three modules were designed for specific fractures involving nasal, orbital, and/or jaw regions (Table 1). Each module takes 2-5 minutes to complete for a total of 2-20 minutes/survey depending on fracture pattern.

1. General Module (IMPACT-G)
  - a. **Target patients:** All maxillofacial trauma patients
  - b. **Number of questions:** 21
  - c. **Structure:** 5-point Likert Scales (except for a single “pain score” from 0-10)
  - d. **Subscales (4):** Overall Facial Appearance, Psychosocial Function, General Symptoms, Pain
2. Nasal Module (IMPACT-N)
  - a. **Target patients:** Fractures of the nasal bones and/or sinuses
  - b. **Number of questions:** 15
  - c. **Structure:** 5-point Likert Scales
  - d. **Subscales (2):** Nasal Function, Nasal Appearance
3. Orbital Module (IMPACT-O)
  - a. **Target patients:** Fractures of the orbital walls or rim
  - b. **Number of questions:** 15
  - c. **Structure:** 5-point Likert Scales
  - d. **Subscales (2):** Orbital Function, Orbital Appearance
4. Jaw Module (IMPACT-J)
  - a. **Target patients:** Fractures of the mandible or upper jaw
  - b. **Number of questions:** 20
  - c. **Structure:** 5-point Likert Scales
  - d. **Subscales (2):** Jaw Function, Jaw Appearance

**Table 1:** User guide for the Integrated Modular Patient-Reported Outcome Assessment for Craniomaxillofacial Trauma (IMPACT).

IMPACT Modules	IMPACT-G	IMPACT-N	IMPACT-O	IMPACT-J
Facial Soft Tissue Injury	X			
Upper Facial Third Fractures				
Frontal Sinus	X	X		
Superior orbital rim	X		X	
Middle Facial Third Fractures				
Nasal bones and/or septum	X			
Facial sinus fractures	X	X		
Naso-orbito-ethmoid	X	X	X	
Orbital rim and/or wall	X		X	
Zygomaticomaxillary complex (ZMC)	X		X	X
Zygomatic arch fracture	X			X
Upper dentoalveolar or palate	X			X
Le Fort I	X	X		X
Le Fort II/III	X	X	X	X
Lower Facial Third Fractures				
Mandible	X			X
Lower dentoalveolar	X			X

This table identifies the appropriate modules to administer to patients with varying patterns of facial trauma. Modules are designed to be assigned by the research team or trained clinical staff before the encounter. These modules function independently, where one patient may only qualify for the IMPACT (ie. soft tissue injury only) while another may warrant all four modules (ie. Le Fort III or panfacial fractures).

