## ABSTRACT

**Context:** Maxillofacial trauma literature is dominated by objective, physician-rated outcomes, leaving a gap in our understanding of the patient experience.

**Objectives:** The primary objective of this study is to validate a novel patient-reported outcome Measure (PROM) for maxillofacial trauma: Integrated Modular Patient-Reported Outcome Assessment for Craniomaxillofacial Trauma (IMPACT).

**Study Design:** Prospective, multi-institutional survey study.

**Setting/Participants:** Patients presenting for routine clinic follow-up for maxillofacial trauma at high-volume trauma centers throughout the United States will be screened. Adults with fractures of the upper face, midface, mandible, and/or facial soft tissue injury within the last 12 months will be included.

**Study Procedures, Interventions and Measures:** Participants providing informed consent will complete the appropriate IMPACT survey modules based on their fracture pattern: IMPACT-N for involvement of the nasal region, IMPACT-O for the orbital region, and/or the IMPACT-J for the jaw. Patients will also complete the 15 Dimension (15D) QOL survey as a control. Surveys will be collected at two consecutive appointments. Independent variables related to the trauma will be abstracted for analysis.

**Main study outcome measures:** The primary objective will be to determine criterion validity of each IMPACT module and subscale via correlation with the 15D (Pearson's r). Secondarily, we will analyze internal validity and reliability (via Cronbach alpha and Item Response Theory [IRT] analysis). Consecutive surveys will be compared for reliability. The minimally clinically important difference (MCID) will be calculated using an anchor-based approach. Finally, IMPACT scores will be analyzed across independent variables including sociodemographic variables, trauma details, and management approach.

---

---

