#### **6.5 Sample Size and Power**

For PROM development, 4-10 participants per item with an absolute minimum of 100 is often recommended for field testing. Therefore, this study will have 150 patients complete each module. Based on a host institution pilot study of 50 patients, the percentage of those being indicated for the IMPACT-N, IMPACT-O, and IMPACT-J were 40%, 30%, and 60%, respectively. Therefore, it is expected that 500 patients with maxillofacial trauma will need to be recruited in order to properly validate the least common IMPACT-O with at least 150 patients. The anticipated nonresponse rate from this pilot study was 33%, so it is expected that a total of 750 patients will need to be invited in order to meet this sample size.

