## **7.6 Screening Strategy**

One member of the research team will screen patients on the upcoming clinic schedule to look for potential participants based on the “chief complaint”. Those with a chief complaint related to maxillofacial trauma will be reviewed for inclusion and exclusion criteria. If satisfied, a REDCap file will then be generated for that patient and the appropriate IMPACT modules will be selected. Patients that do not satisfy inclusion and exclusion criteria based on chart review will not be included and no information will be recorded.

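### Table 1 as printed gives nasal bone and septum fractures the general module only, against the protocol's own definition of who should receive IMPACT-N

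*Protocol*

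**What the plan says.** Protocol 5.1.1 describes one general module for every patient and three regional modules. Item 2a gives the target of the nasal module, IMPACT-N, as "Fractures of the nasal bones and/or sinuses". The abstract states the same rule more broadly: "IMPACT-N for involvement of the nasal region".

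Table 1 in the same section turns these definitions into an assignment grid. Its row "Nasal bones and/or septum" has one mark, under IMPACT-G. The cells for IMPACT-N, IMPACT-O and IMPACT-J are blank.

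The text below the table makes the grid operative: "This table identifies the appropriate modules to administer to patients with varying patterns of facial trauma". Its example of a patient who needs only the general module is someone with soft tissue injury alone; a nasal fracture is not mentioned. Section 7.6 has modules chosen when the patient is screened: "the appropriate IMPACT modules will be selected". Section 3.2.2 sets the stopping rule: "Recruitment will stop when 150 subjects have completed each IMPACT Module". Section 6.5 bases the enrolment figure on a pilot of 50 patients in which "the percentage of those being indicated for the IMPACT-N, IMPACT-O, and IMPACT-J were 40%, 30%, and 60%, respectively".

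**The concern.** The first-named target of the nasal module is not assigned the nasal module. Two rules in one section give different answers for the same patient, and the one designated for staff to use is the one that leaves the module out.

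If the table is followed, the missing answers cannot be recovered in the analysis, because the questions were never put. The correlation of IMPACT-N with the 15D (the primary endpoint for this module), its reliability and its MCID would come from patients with sinus, naso-orbito-ethmoid and Le Fort fractures, alone or combined with a nasal bone fracture. The results would still be reported for a module said to cover nasal bone fractures in general. If some of the roughly 10 sites follow item 2a and others follow the table, the make-up of the IMPACT-N sample would also differ by site.

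**Working it through.** **1. The table set against the definitions.** Table 1 has one soft tissue row and 13 fracture rows.

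| Check | Count |
|---|---|
| Fracture rows | 13 |
| With at least one regional module | 12 |
| With IMPACT-N | 5 (frontal sinus, facial sinus, naso-orbito-ethmoid, Le Fort I, Le Fort II/III) |
| With no regional module | 1 (nasal bones/septum) |

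Item 2a names two targets, nasal bones and sinuses. The sinus rows carry the IMPACT-N mark and the nasal bone row does not. The conflict with item 2a is explicit for nasal bones. Septum is not named there and is covered only by the abstract's reference to the nasal region.

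**2. Who is left out.** A nasal bone fracture combined with any of the five marked injuries still triggers IMPACT-N. The omitted group is patients with a nasal bone or septum fracture and none of those five. It includes patients who also have, for example, a mandible fracture: they would receive IMPACT-J but not IMPACT-N.

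**3. The plan's own enrolment figures (6.5).** The inputs are 150 completers per module, pilot shares of 40% (IMPACT-N), 30% (IMPACT-O) and 60% (IMPACT-J), and 33% nonresponse.

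- Least common module, IMPACT-O: 150 / 0.30 = 500 enrolled, as stated.
- Invited: 500 / 0.67 = 746, stated as 750 (exactly 750 if 33% stands for one third).
- IMPACT-N: 150 / 0.40 = 375 enrolled, below 500, so IMPACT-O is the limiting module.

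**4. What the table could do to enrolment.** The pilot shares correspond to 0.40 × 50 = 20 patients for IMPACT-N and 0.30 × 50 = 15 for IMPACT-O. The protocol does not say which rule produced the 40%.

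- If it was counted under Table 1 as printed, nothing in step 3 changes.
- If it was counted under item 2a, let f be the share of those 20 whose only nasal-region injury is a nasal bone or septum fracture. The protocol does not give f; 10% to 50% is assumed here. Enrolment needed = max(150 / 0.30, 150 / [0.40 × (1 − f)]).

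| f | Patients of 20 | Needed for IMPACT-N | Enrolment needed | Invited (÷ 0.67) |
|---|---|---|---|---|
| 10% | 2 | 150 / 0.36 = 417 | 500 | 746 |
| 25% | 5 | 150 / 0.30 = 500 | 500 | 746 |
| 40% | 8 | 150 / 0.24 = 625 | 625 | 933 |
| 50% | 10 | 150 / 0.20 = 750 | 750 | 1,119 |

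IMPACT-N replaces IMPACT-O as the limiting module only when f exceeds 25%. Even then the stopping rule in 3.2.2 would lengthen recruitment rather than leave the module short of 150.

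**The case against.** The finding rests on one absent mark in a table read from a PDF, and a single character can be lost without disturbing other rows. This stands as a limit on certainty. The other 12 fracture rows read coherently, including those with several marks, and the nasal row shows no shift of columns, but neither point rules out a lost mark.

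A second argument is that everything else in the protocol points the same way, so trained staff would probably notice the gap and give the module anyway. Sections 4.1.1 and 7.6 do not cite Table 1 when they describe assignment. That is fair, and the loss of data does depend on the cell being followed literally. But giving the module would mean departing from the grid that the protocol designates for assignment, and nothing ensures that every site would do so.

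Third, the target lines are not an exact key to the table: item 4a names the mandible and upper jaw, yet Table 1 also gives IMPACT-J to zygomatic arch fractures. That discrepancy adds patients beyond the stated target. The nasal row removes patients whom the target names, which is a different matter.

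Finally, the enrolment scenarios depend on an unknown f and on how the pilot was counted, and no size or direction of effect on the correlation can be shown. Both points are correct. The scenarios are illustrative, and the case rests on the composition of the sample.

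**Conclusion.** The concern holds. As printed, Table 1 contradicts item 2a of 5.1.1 and the abstract, and it does so in the grid that determines which questionnaires a patient receives. It affects 1 of 13 fracture rows and part of one of the two named IMPACT-N target groups.

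The main consequence, if the table is followed, is that IMPACT-N is validated without patients whose only nasal-region injury is a nasal bone or septum fracture. The number of IMPACT-N completers is protected by the stopping rule; their representativeness is not. An effect on the planned 500 enrolled arises only if the pilot's 40% was counted under item 2a and f exceeds 25%, and the protocol establishes neither.

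Confidence is medium, because the original table has to be checked for a lost mark. The point should be fixed: it touches the primary endpoint of one of the four modules and cannot be repaired later for surveys already completed without IMPACT-N.

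**What to change.** 1. Check the original Table 1 for a mark lost in conversion. If the mark is there, no change is needed.
2. If the cell is blank, add the IMPACT-N mark to the nasal bones/septum row so that it agrees with item 2a and the abstract. Naming the septum in item 2a would complete the match.
3. Check that each site's module-assignment setup, on tablet or paper, follows the corrected row.
4. If patients were already enrolled under the printed table, report how many with nasal bone or septum fractures did not receive IMPACT-N.

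The cost is one table cell, a few words in item 2a and a setup check at each site. Affected patients complete one more module of 2 to 5 minutes at each survey. If the pilot's 40% was counted under item 2a, the 500 and 750 in 6.5 stand after the correction: IMPACT-N would be expected to yield 500 × 0.40 = 200 completers. If it was counted under the printed table, the corrected row can only add IMPACT-N patients, so 500 remains enough.

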### 5.1.2 15D Survey

The 15D is a well-established survey to assess QOL over numerous medical and/or surgical patients. It has 15 questions each on unique 5-point Likert scale and all related to some QOL theme. This survey has previously been used in maxillofacial trauma. It was chosen as a control for this study given its robust validity for measuring QOL and several individual themes that are specifically related to maxillofacial trauma such as eating, drinking, speech, anxiety, and depression.

### 5.2 Safety Evaluation

As an observational survey study, there are no expected adverse events; however, patients will be observed per regular clinical care for any adverse event associated with their facial trauma.

---

## 6 STATISTICAL CONSIDERATIONS

### 6.1 Primary Endpoint

The primary endpoint pertains to the primary objective, determining the validity of each IMPACT module and subscale for measuring QOL in patients with maxillofacial trauma. This will be determined by correlating the IMPACT scores with the corresponding 15D score, controlling for any independent predictors of IMPACT and 15D scores.

### 6.2 Secondary Endpoints

1. Identification of independent predictors of IMPACT scores including baseline sociodemographic, injury, and treatment variables.
2. Determine the reliability of IMPACT scores.
3. Calculate the change in IMPACT scores at subsequent clinic visit(s).
4. Calculate the MCID for each IMPACT module and subscale.

### 6.4 Statistical Methods

All analysis will be performed by the host institution. Effect sizes with 95% confidence intervals (CI) will be provided for every applicable measurement. The analytical plan will be reviewed by professional biostatisticians at the host institution.

#### 6.4.1 Baseline Data

The following chart review variables will be abstracted after informed consent is obtained and the initial survey is completed. This data will be summarized descriptively with average, median, range, interquartile range, and standard deviation, as appropriate. Each variable will then be tested for association with IMPACT scores on univariable analysis. Clinically or statistically significant variables will then be included in subsequent multivariable testing.

---

---

- Sociodemographic data: Age, sex, race, ethnicity, marital status, smoking status, payor type (private, medicare, Medicaid, government, none / self-pay, or other), and Social vulnerability index (SVI) values based on home address.
  - SVI: A measure of social vulnerability assigned to each zip code or census tract by the Center for Disease Control and Prevention.
- Trauma data: Mechanism, concomitant multisystem trauma, airway status, level of care (discharged from emergencet room, floor/stepdown admit, intensive care admit), presenting signs or symptoms (cranial nerve weakness, trismus, malocclusion, visual impairment), description of facial trauma, comprehensive facial injury (CFI) score, and Facial Injury Severity Score (FISS).
  - CFI: An objective scale based on maxillofacial imaging and clinical exam providing an integer that represents fracture severity by correlating it with the operative time for repairing each fracture.
  - FISS: An objective scale based on maxillofacial imaging and clinical exam providing an interger that represents the objective severity of facial trauma by correlation with the cost of management.
- Management data: Treatment (observation, bedside intervention, or surgical repair), type of surgical repair (closed reduction, open reduction, internal fixation, external fixation, and maxillomandibular fixation [MMF]), hospital length of stay (days), disposition (home versus medical facility)
- Objective complications: Wound infection or dehiscence, Malunion or nonunion, hardware extrusion, or any unplanned return to the emergency department, admission or reoperation related to the facial injury.
- Survey metadata: time from trauma to survey (days), time from intervention to survey (if applicable; days), presence of maxillomandibular fixation at the time of the survey.

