### **2.2 Secondary Objectives**

1. Analyze IMPACT module and subscale scores across baseline sociodemographic, injury, and treatment variables in order to understand which factors influence QOL.
2. Analyze the reliability of each IMPACT module and subscales.
3. Determine the sensitivity to change for IMPACT modules and subscales.
4. Calculate the minimally clinically important difference (MCID) for each IMPACT module and subscales.

---

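### Complications are abstracted after the initial survey with no date or cut-off relative to it, so a later complication can be counted as a predictor of an earlier IMPACT score

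*Protocol*

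**What the plan says.** Protocol 6.4.1, headed as baseline data, fixes the earliest time of chart review: "The following chart review variables will be abstracted after informed consent is obtained and the initial survey is completed". It gives no latest time and no cut-off for events.

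Three groups in its list matter here:

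- Treatment: "Management data: Treatment (observation, bedside intervention, or surgical repair), type of surgical repair".
- Complications: "Objective complications: Wound infection or dehiscence, Malunion or nonunion, hardware extrusion, or any unplanned return to the emergency department, admission or reoperation", where related to the facial injury. No date, interval or as-of-survey condition is attached.
- Timing relative to the survey, the last item being fixation status on that day: "Survey metadata: time from trauma to survey (days), time from intervention to survey (if applicable; days), presence of maxillomandibular fixation at the time of the".

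On use, the section says: "Each variable will then be tested for association with IMPACT scores on univariable analysis". Variables judged clinically or statistically significant go on to multivariable testing. Section 6.4.4, item 1, carries the independent predictors into the regression for the primary endpoint, and 6.4.3 controls for every variable that influences IMPACT scores. Section 2.2 gives the purpose of the predictor analysis: "in order to understand which factors influence QOL".

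Eligibility requires an injury "within 12 months of recruitment date" (3.3.1). Under 4.1 the two surveys may fall at any consecutive follow-up visits in the first year, and under 3.2.1 participation lasts up to 3 months.

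**The concern.** A predictor that is meant to explain a score should be in place when the score is given. The complication list includes "hardware extrusion, or any unplanned return to the emergency department, admission or reoperation related to the facial injury". Several of these can occur weeks or months after a first clinic survey. If they are abstracted whenever the chart happens to be read, the complication variable mixes three things: complications already present at the survey, complications that came later, and how long the chart was left to accumulate events.

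Two errors can follow, in opposite directions. Later complications unrelated to the score dilute a real association. If patients who report poor scores are more likely to return or be reoperated on afterwards, an association appears although the complication did not affect the score. Either result could be reported as a factor that influences quality of life, and a variable selected for the wrong reason would then enter the adjusted model for the primary endpoint.

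This is a matter of data collection, not only of analysis. Under 7.3.2 each site sends a de-identified spreadsheet at the end, and under 6.4 the host does all the analysis. Timing that was not captured at the site cannot be restored by an analysis rule at the host.

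**Working it through.** The protocol gives no figure on this point, so there is none to reproduce. The check sets the provisions side by side and then shows the possible size under stated assumptions.

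**1. Is each variable tied to the survey date?**

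| Variable in 6.4.1 | Link to the survey |
|---|---|
| Injury | Days from trauma to survey |
| Treatment | Days from intervention to survey, if applicable; no rule for an intervention that follows the survey |
| Maxillomandibular fixation | Presence at the survey |
| Complications | None |

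Complications are the only one of these four with no link.

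**2. Can the collected timing supply the order?** Time from trauma to survey measures how long a patient was at risk before the survey. That varies widely: a survey at 2 weeks against one at 10 months (10 × 52/12, about 43 weeks) is a ratio of 43/2, roughly 20-fold. Including this variable in the model can adjust for that difference. It cannot show whether a given complication fell before or after the survey, nor how long after the survey the chart was read.

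**3. Dilution (assumed inputs).** Suppose complications present at the survey worsen the score by 10 points, later ones are unrelated to it, and a share q of recorded complications is later. Observed difference = 10 × (1 − q).

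- q = 25%: 10 × 0.75 = 7.5 points
- q = 50%: 10 × 0.50 = 5.0 points
- q = 75%: 10 × 0.25 = 2.5 points

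**4. Reversed order (assumed inputs).** Suppose complications have no effect on the score, all follow the survey, and the score SD is 20. The log-odds of a later event are ln(0.12/0.88) + ln(OR) × s, where s is the standardised score (higher is worse). The observed difference is 20 × (mean s with an event − mean s without). A simulation of 2,000,000 patients gives:

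| OR per SD of worse score | Event rate | Spurious difference (points) | Rough check, 20 × ln(OR) |
|---|---|---|---|
| 1.0 | 12.0% | about 0 | 0 |
| 1.25 | 12.2% | 4.4 | 4.5 |
| 1.5 | 12.7% | 8.0 | 8.1 |
| 2.0 | 13.9% | 13.1 | 13.9 |

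None of q, the 10-point effect, the SD, the event rate or the odds ratios comes from the protocol. The calculations show direction and a plausible range, not an estimate for this study.

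**The case against.** The sentence on abstraction says when the chart may be opened, not which events count. Reading a chart after a survey is compatible with recording only what came before it, and the section is headed as baseline data. This is correct: late abstraction is not in itself the fault. The fault is that nothing restricts complications to those that precede the survey, and a site following the text could enter later ones in good faith.

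A reader might infer that treatment has the same defect, so that pre-operative scores are inevitably pooled with post-operative ones. The documents do not support that. Days from intervention to survey and fixation status at the survey are both collected, so a later intervention can be identified. Only a rule for coding it is missing.

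A reader might also infer that the primary validity result is compromised. The criterion in 6.4.3 is Pearson's r with the 15D, and a complication's date does not change that coefficient. Only the adjusted regression can be touched, and the effect there has not been quantified.

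Two further points stand. The secondary objective in 2.2 names sociodemographic, injury and treatment variables, not complications; complications enter through the instruction in 6.4.1 to test every listed variable. The protocol also does not say which of the two surveys supplies the score in the predictor models, so the rule has to be stated separately for each survey.

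That later surveys allow more time for complications is not an error in itself, and time from trauma to survey can adjust for it.

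**Conclusion.** The point holds for complications. As written, they may be abstracted at any time after the initial survey, carry no date or cut-off, and are tested as predictors of IMPACT scores, so the order of cause and effect is not protected. For treatment only a coding rule is lacking.

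The consequence is confined to the predictor analysis and to the adjusted regression that inherits its selected variables. That some associations will run backwards is a possibility that the plan leaves open, not something the documents establish. The size cannot be derived from them: the dilution to 7.5, 5.0 or 2.5 points and the spurious differences of about 4 to 13 points rest wholly on the assumptions given with them. This is an inexpensive improvement that should be made before sites abstract data. It does not undermine the main validation result.

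**What to change.** In section 6.4.1:

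- For each complication, record the date or the signed interval in days to each survey. The interval matches the existing survey metadata and suits the de-identified export in 7.3.2.
- Let a complication predict a survey's score only if it occurred on or before that survey.
- Code treatment as of the survey being analysed, using the time from intervention to survey already collected. An intervention after that survey is coded as not yet treated.
- Include time from trauma to survey in every model with a complication or treatment term.
- Let events between the two surveys predict the second score or the change in score, but not the first score.

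The cost is one extra field per complication in a chart that is already being reviewed, with no patient contact. Somewhat fewer complications will count, which reduces precision for that variable group.
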